5.3 OTHER ANALYSES OF OFF-TREATMENT FOLLOW-UP DATA

A descriptive summary of values during on-treatment period compared with values during off-treatment follow-up period will be shown using boxplots for the following endpoints:

- Annualized percent change in ventricle volume – maximum on-treatment versus maximum off-treatment value will be used
- CSF protein – maximum on-treatment versus last off-treatment value will be used
- CSF Leukocytes – maximum on-treatment versus last off-treatment value will be used

For these analyses the off-treatment period will start at the day after the last dose of study treatment plus 5 months (152 days).

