2. STUDY DESIGN

[figure not shown]
Approximately 801 patients will be enrolled in Study BN40423 under Protocol Version 4 and onwards. Prospective patients will undergo screening assessments during a 4-week screening period.

Upon completion of the screening period, eligible patients will be randomized in a 1:1:1 ratio to receive 120 mg RO7234292 Q8W, 120 mg RO7234292 Q16W, or placebo Q8W by IT injection. To maintain the study blind and integrity, patients in the 120 mg RO7234292 Q16W arm will also receive placebo every 8 weeks (i.e., alternating doses of active drug and placebo every 8 weeks).

Following the iDMC recommendation and Sponsor's decision to discontinue study treatment in this study, as of 22 March 2021, all patients will transition to the Early Treatment Termination (ETT) schedule within 56 days after treatment discontinuation as shown in [Figure 1](#).

The language used in this SAP supersedes that in the protocol and protocol synopsis.

Figure 1 Visit Schedule Scenarios for Early Treatment Termination (Applicable to All Patients from 22 March 2021)

EoT=end of treatment; ETT=early treatment termination; FU=follow-up.

^a The ETT visit should be performed within 56 days of the decision to discontinue study treatment. A telephone safety follow-up call will be conducted every 8 weeks between the clinic visits, to check for any change in patient status since the patient's last visit.

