2.2 ENDPOINTS

Following the iDMC recommendation and Sponsor's decision to discontinue study treatment in this study, as of 22 March 2021, only data collected up to 22 March 2021 will be used to evaluate the efficacy of RO7234292. By that date, approximately 80% of the participants reached their Week 69 visit, therefore the efficacy and biomarker outcome measures will be evaluated based on change from baseline at Week 69 (rather than change from baseline at Week 101).

However, all outcome measures are listed below as planned per protocol (i.e., referring to change from baseline at Week 101).

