3.2 DATA MONITORING

An iDMC will be employed to monitor and evaluate cumulative patient safety throughout the study. It is anticipated those safety reviews will occur approximately every 4 months (further details are provided in a separate iDMC charter).

Following the iDMC recommendation to halt the dosing in Study BN40423, the scope of the iDMC has been revised and it is now focusing on a comparison of the on-treatment period (data collected up to treatment termination) against the off-treatment follow-up period (data collected after treatment termination). Further details are provided in the updated iDMC charter.

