4.9 SAFETY ANALYSES

Following the iDMC recommendation, effective 22 March 2021, no further study treatment was administered in this study. Patients in the study were continued to be followed for safety and efficacy outcomes until study completion.

All safety endpoints will be analyzed overall, i.e., disregarding if data was collected during on-treatment period or during off treatment follow-up period. On-treatment period is defined as time from first dose to last dose plus 5 months. Off-treatment follow-up period is defined as the time more than 5 months after last dose of study drug.

Analyses addressing the on-treatment period and off-treatment follow-up period are described in Section 5.

For all safety endpoints, if not stated otherwise, the baseline will be defined as the last assessment prior to the first lumbar puncture procedure or last assessment on Day 1, whichever occurred first.

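### SAP Section 5.3 sets each patient's on-treatment maximum against one last off-treatment value for CSF protein and leukocytes, so the boxplots would suggest a fall even if nothing changed

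*SAP*

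**What the plan says.** Section 5.3 of the SAP (Version 3) introduces the display in these terms: "A descriptive summary of values during on-treatment period compared with values during off-treatment follow-up period will be shown using boxplots". Three endpoints follow. For CSF protein and for CSF leukocytes the rule is "maximum on-treatment versus last off-treatment value will be used". For annualized change in ventricle volume it is "maximum on-treatment versus maximum off-treatment value will be used". No reason is given for the difference.

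The off-treatment period in this section begins once 152 days have passed since the last dose. This agrees with Section 4.9: "On-treatment period is defined as time from first dose to last dose plus 5 months". The on-treatment maximum is therefore taken over the whole dosing period and the five months after it.

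Section 5.3 sets no test, responder rule or threshold. It does not say whether the boxes are shown by arm, or whether a patient must have values in both periods to be plotted.

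**The concern.** The two boxes hold different kinds of quantity. One holds each patient's extreme over many samples, the other a single reading. Some of any patient's maximum is chance, so a later single value tends to lie below it whether or not the underlying level has moved. The gap widens with the number of on-treatment samples and with within-patient variability, so it also depends on time on treatment and need not be equal across arms.

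What is at stake is how CSF protein and leukocytes are read after dosing stopped. Section 5.1 models cUHDRS and MRI, and Section 5.2 models cUHDRS and MoCA. Only Section 5.3 sets the two CSF measures on treatment against off treatment. A reader of that figure could see a fall that the rule itself produced, and a persistent elevation would be understated.

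**Working it through.** The SAP gives no figure for this comparison, so there is none to reproduce. The check asks what the rule yields in a patient whose CSF level does not change.

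**Inputs**
- Number of on-treatment CSF samples, k: not stated for Protocol Version 4 onwards. The assessment schedule attached to SAP Version 1 belongs to Protocol Version 3 and does not apply.
- Assumption: one sample at each post-baseline week listed in Appendix 1 for endpoints other than UHDRS and the global impression scales. Weeks 5, 13, 21, 29, 37, 45, 53, 61 and 69 give k = 9. Stopping at Week 37 gives k = 5; going on to Week 101 gives k = 13.
- k = 9 is a reasonable centre because Section 2.2 says of the dosing halt: "By that date, approximately 80% of the participants reached their Week 69 visit".

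**Protein (continuous)**

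If the k on-treatment values and the one off-treatment value are exchangeable within the patient, each of the k + 1 is equally likely to be the largest. So P(last off-treatment < on-treatment maximum) = k/(k + 1), whatever the patient's own level.
- k = 5: 5/6 = 0.833
- k = 9: 9/10 = 0.900 (simulated 0.901)
- k = 13: 13/14 = 0.929

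Variations at k = 9:
- Serial correlation of 0.3, 0.6, 0.8 or 0.9 between visits, with the off-treatment value three visits after the last on-treatment one: 0.88, 0.85, 0.81, 0.79.
- Rounding to 0.01 g/L, with an assumed within-patient SD of 0.02 to 0.10: 0.85 to 0.89.

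For normal, independent values, the on-treatment box sits above the off-treatment box by the expected maximum of k standard normals, in within-patient SDs: 1.16 at k = 5, 1.49 at k = 9 and 1.67 at k = 13.

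An illustration uses the upper normal limit of 0.5 g/L in the CSF table of Section 4.9.3. Assume a patient with constant mean 0.45 and within-patient SD 0.05. The limit is 1 SD above the mean, so a single value exceeds it with probability 0.16. The maximum of 9 exceeds it with probability 1 − 0.841^9 = 0.79.

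**Leukocytes (low integer counts)**

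Ties matter here. With Poisson counts, P(last < maximum) = Σ p(y)[1 − F(y)^k]. At k = 9:

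| Mean count | Last lower | Tie | Last higher |
|---|---|---|---|
| 0.1 | 0.54 | 0.42 | 0.04 |
| 0.25 | 0.74 | 0.22 | 0.04 |
| 1 | 0.82 | 0.12 | 0.06 |
| 2 | 0.84 | 0.09 | 0.07 |
| 5 | 0.87 | 0.06 | 0.07 |

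Over the same means, the first column runs from 0.36 to 0.79 at k = 5 and from 0.66 to 0.90 at k = 13. In every case a lower last value is far more likely than a higher one.

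**Like for like**

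One on-treatment value against one off-treatment value, continuous and unchanged: 0.50.

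**The case against.** The strongest reply is that this is a descriptive boxplot within an analysis that Section 2.4 calls exploratory. No test, decision rule or efficacy conclusion depends on it. That stands, and it sets the severity.

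A reader might infer that about nine in ten unchanged patients would be declared recovered. The documents do not support that. Section 5.3 defines no recovery, and two boxes classify no individual patient. The 90% rests on an assumed k = 9 and on continuous, exchangeable values, and it is too high for leukocyte counts. The upward shift of the on-treatment box does not depend on classifying patients, and it remains.

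A reader might also infer that the data monitoring committee relies on this figure, because Section 3.2 says "it is now focusing on a comparison of the on-treatment period (data collected up to treatment termination) against the off-treatment follow-up period". That section points to a separate charter, divides the periods at treatment termination without the 152 days, and mentions neither CSF nor Section 5.3. The link is not established.

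Other summaries help in part. Section 4.9.3 plans laboratory values and change from baseline at each visit by treatment group, and counts abnormal CSF values by treatment and visit. Section 4.9 includes data from both periods. A lasting difference between arms could show there. But these summaries follow study visit, not time since last dose, so one visit can mix patients on and off treatment.

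The ventricle row is not proof that the CSF rows are a slip. Maximum against maximum is also tilted when the periods hold different numbers of values: with 9 on and m off, the probability is 9/(9 + m), or 0.90, 0.82 and 0.75 for m = 1, 2 and 3.

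Finally, worst value reached against final state is a legitimate thing to describe. It needs to be labelled as that, and it cannot stand in for a comparison of the two periods.

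**Conclusion.** The rule is wrong as written for an on- versus off-treatment comparison. With no true change it yields an apparent fall. Under the stated assumptions, at about 9 on-treatment samples, roughly 80-90% of unchanged patients would have a lower last protein value. About 55-85% would have a lower leukocyte count, with ties making up most of the rest at low means. Varying k from 5 to 13 gives 83-93% for protein without serial correlation. The leukocyte figure drops to 36% if there are only 5 samples and nearly all counts are zero.

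The direction follows from the stated rule alone. The size rests on the assumed number of samples, the assumed distributions and a stable within-patient level. Severity is moderate: this is a descriptive, exploratory safety display, partly offset by the visit summaries by arm, but it is the only planned comparison of the two periods for these measures.

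**What to change.** Amend Section 5.3 for CSF protein and leukocytes as follows.

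- Restrict the comparison to patients with a value in both periods, and state how many there are in each arm.
- Plot the same kind of statistic on both sides, for example the last value taken at or before the last dose against the last off-treatment value, or mean against mean. A plain last on-treatment value would not do, because under the 152-day rule it may come from up to five months after dosing ended.
- Show the boxes by arm with placebo as reference, and add the within-patient change.
- Keep the on-treatment maximum as a separate display, labelled as a description of peak values.

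The cost is SAP wording and one or two re-programmed figures, with no new data. The downside is that the last value at or before the last dose may miss an earlier peak, which the separate peak display covers.

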Appendix 1 Reporting Windows by Endpoints

All visits are used as labeled in the data.

Data collected at the early termination visit (for endpoints Unified Huntington's Disease Rating Scale [UHDRS], Clinical Global Impression, Change Scale [CGI-C], Patient Global Impression of Change [PGI-C], and Companion-Reported Global Impression, Change (CrGI-C): also unscheduled visits) will be mapped to the visits applying reporting windows depending on the endpoint as described in [Table 1](#).

If there are two or more assessments for an endpoint within the same visit due to the remapping of early termination or unscheduled visits, the mean of all assessments within the same visit will be considered in the analysis. If there are two or more assessments for an endpoint within the same visit but not due to the remapping of early termination or unscheduled visits, the last available assessment will be considered in the data analysis.

Table 1 Reporting Windows by Endpoints

Scheduled Week	Reporting Window (based on study day)			Reporting Window (based on study day)		
	All Endpoints except UHDRS, CGI-C, PGI-C and CrGI-C			Endpoints UHDRS, CGI-C, PGI-C and CrGI-C		
1	1	to	13	1	to	13
5	14	to	55	14	to	83
13	56	to	111			
21	112	to	167	84	to	195
29	168	to	223			
37	224	to	279	196	to	307
45	280	to	335			
53	336	to	391	308	to	419
61	392	to	447			
69	448	to	503	420	to	531
77	504	to	559			
85	560	to	615	532	to	643
93	616	to	671			
101	≥ 672			≥ 644		

CGI-C = Clinical Global Impression; Change Scale, CrGI-C = Companion-Reported Global Impression, Change; PGI-C = Patient Global Impression of Change; UHDRS = Unified Huntington's Disease Rating Scale.

Signature Page for: System identifier:RIM-CLIN-439389
Statistical Analysis Plan - BN40423 - Published

Approval Task	 Scientific content approver 12-May-2022 17:17:08 GMT+0000
---------------	--

STATISTICAL ANALYSIS PLAN

TITLE: A RANDOMIZED, MULTICENTER, DOUBLE-BLIND, PLACEBO-CONTROLLED, PHASE III CLINICAL STUDY TO EVALUATE THE EFFICACY AND SAFETY OF INTRATHECALLY ADMINISTERED RO7234292 (RG6042) IN PATIENTS WITH MANIFEST HUNTINGTON'S DISEASE

PROTOCOL NUMBER: BN40423 version 1-3

STUDY DRUG: RO7234292

VERSION NUMBER: 1

IND NUMBER: 137873

EUDRACT NUMBER: 2018-002987-14

SPONSOR: F. Hoffmann-La Roche Ltd

PLAN PREPARED BY: [REDACTED] Ph.D., [REDACTED], Ph.D.

DATE FINAL: See electronic date stamp below

STATISTICAL ANALYSIS PLAN APPROVAL

Date and Time(UTC)	Reason for Signing	Name

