2.1 PROTOCOL SYNOPSIS

Please refer to Protocol Version 6 for the protocol synopsis. For additional details, see the Schedule of Assessments in Protocol Version 6, Appendix 1a and the Schedule of Assessments for Early Treatment Termination in Protocol Version 6, Appendix 1b.

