4.4.3 Secondary Efficacy Endpoints

The continuous secondary efficacy endpoints will be analyzed via an MMRM as described in Section [4.4.2](#).

Similar as for the primary endpoint, the MMRM analysis will be performed instead of per protocol planned analyses via ANCOVA. For these analyses, least squares means for the treatment differences at Week 69 and corresponding 95% CIs will be reported. No adjustments for multiple comparisons will be incorporated into the analyses, especially the testing strategy described in Protocol Section 6.3 is not considered for any analyses.

Change from baseline at Week 69 will be analyzed for the following secondary endpoints:

- TFC
- TMS
- SDMT
- SWR Test
- CGI-S

The categorical secondary endpoints will be analyzed descriptively and by means of logistic regression including treatment (categorical), CAG repeat length, and CAP score as covariates.

- Analyses will be conducted for the following categorical secondary endpoints:
Proportion of patients with a decrease from baseline of at least 1 point on the TFC at Week 53 and at Week 69
- Proportion of patients with a decline from baseline of at least 1.2 points on the cUHDRS at Week 53 and at Week 69
- Proportion of patients with an unchanged or improved score on the CGI-C score from baseline at Week 53 and at Week 69

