5.1 MIXED MODEL REPEATED MEASUREMENTS

Data collected up to Week 101 will be analyzed by an MMRM model as defined in Section 4.4.2. Different approaches will be defined for these MMRM analyses:

1. ITT analysis will include all patients in the ITT population
2. iDMC ad-hoc completer analysis will include patients who completed Week 101
3. Completer analysis will include patients who completed Week 101 and who had their last dose of study drug more than 5 months (> 152 days) prior to their Week 101 visit

The statistical modeling will be applied to the following endpoints:

- cUHDRS and its individual components
- MRI (BSI data, annualized percentage change from baseline)
- cUHDRS and components for age and CAP subgroups (if number of patients in the subgroup is sufficiently large, especially for the completers analyses)

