- ^m Serum chemistry panel: includes bicarbonate or total carbon dioxide (if considered standard of care for the region), sodium, potassium, chloride, glucose, BUN or urea, creatinine, total protein, albumin, phosphorus, calcium, total and direct bilirubin, ALP, ALT, AST, uric acid, gamma-glutamyl transferase, and CPK.
- ⁿ All women of childbearing potential will have a serum pregnancy test at screening. Urine pregnancy tests will be performed at specified subsequent visits. If a urine pregnancy test is positive, it must be confirmed by a serum pregnancy test.
- ^o Urinalysis includes dipstick (pH, specific gravity, glucose, protein, ketones, blood) and microscopic examination (sediment, RBCs, WBCs, casts, crystals, epithelial cells, bacteria).
- ^p At the Week 37 visit, PK samples will be collected prior to dosing and at 1, 2, and 4 hours post-dose. All patients will remain in clinic at least 4 hours after lumbar puncture.
- ^q At Weeks 13, 37, and 69 and at the EoT visit, the MRI should be scheduled to occur before the lumbar puncture. It can be scheduled in the days prior to the lumbar puncture (provided it occurs within the visit window). After patient enrollment, the MRI scan should be performed 7–14 days prior to the lumbar puncture to allow time for re-scanning if the quality of the initial MRI is inadequate. MRI should take place as early as

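### Appendix 1 windows early-termination CGI-S (and PGI-S) 8-weekly while UHDRS, CGI-C and PGI-C get 16-week windows; if CGI-S follows the UHDRS calendar, about half of those values land on visits with no scheduled CGI-S

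*SAP*

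**What the plan says.** All references are to SAP Version 3 unless stated.

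- **Which data are windowed.** Appendix 1 begins "All visits are used as labeled in the data". Early-termination data are the exception: they "will be mapped to the visits applying reporting windows depending on the endpoint as described in" its Table 1. For UHDRS, CGI-C, PGI-C and CrGI-C, unscheduled visits are remapped as well.
- **Two columns.** One column, for UHDRS, CGI-C, PGI-C and CrGI-C, has windows around Weeks 5, 21, 37, 53, 69, 85 and 101. The other, headed "All Endpoints except UHDRS, CGI-C, PGI-C and CrGI-C", has windows around every 8-weekly visit. The Week 69 row reads "69 448 to 503 420 to 531": 56 days in the 8-week column and 112 days in the 16-week column. CGI-S and PGI-S are not among the named exceptions, so they take the 8-week column.
- **Analysis.** Section 4.4.3 states "The continuous secondary efficacy endpoints will be analyzed via an MMRM as described in Section" 4.4.2, and lists CGI-S at Week 69. That model has visit as a categorical factor, a visit-by-treatment interaction and an unstructured covariance, with TOEPH, ANTE(1) and CSH as ordered fallbacks. Section 4.4.4 applies the same model to the exploratory endpoints, which include PGI-S.
- **Schedule.** For the analysed cohort, Section 2.1 sends the reader elsewhere: "see the Schedule of Assessments in Protocol Version 6, Appendix 1a". The only schedule in the file is in SAP Version 1, Appendix 2. It is that of Protocol Version 3, for the Original Design Cohort, and there the CGI-S row carries the same marks as the SDMT and SWR rows.

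**The concern.** The table separates CGI-S from CGI-C, and PGI-S from PGI-C, without giving a reason. Take an early-termination visit on Day 430. TFC and CGI-C are filed under Week 69; CGI-S from the same day is filed under Week 61. If CGI-S is collected on the UHDRS calendar, Week 61 has no scheduled CGI-S.

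The plan does not say what happens to such a value. If only scheduled visits are modelled, it is dropped, and the loss falls entirely on early terminators. If Week 61 becomes a level of the visit factor, only early terminators fill it. Either way the CGI-S model uses these patients differently from the TFC, cUHDRS and CGI-C analyses. The choice would be made at programming stage by a sponsor that Section 1 says is already unblinded, so it should be fixed in the text.

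**Working it through.** **1. Reproduce the windows.** Take nominal day = 7 × (week − 1) and let each window meet its neighbour midway. This reproduces all 14 windows of the 8-week column and all 8 of the 16-week column. For Week 69 the nominal day is 7 × 68 = 476.
- 8-week column: (420 + 476)/2 = 448 to (476 + 532)/2 − 1 = 503.
- 16-week column: (364 + 476)/2 = 420 to (476 + 588)/2 − 1 = 531.

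Both match Table 1, so the table is internally sound. The question is only which endpoints belong in which column.

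**2. Days on which the columns disagree, Days 14-643 (630 days).**
- Days 14-83 (Week 5 in the 16-week column): Days 56-83 go to Week 13, 28 days.
- Each of the five 112-day windows (Weeks 21, 37, 53, 69, 85): 56 days go to a neighbouring 8-weekly visit, 5 × 56 = 280.
- Total 28 + 280 = 308; 308/630 = 49%.

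The labels received on those days are Weeks 13, 29, 45, 61 and 77 (56 days each) and Week 93 (Days 616-643, 28 days). Extending to Day 671 adds 28 days (Week 93 against Week 101): 336/658 = 51%. Stopping at Day 531 gives 252/518 = 49%.

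**3. Week 69 alone.** Of Days 420-531 (112 days), Days 420-447 go to Week 61 and Days 504-531 to Week 77: 28 + 28 = 56, or 50%.

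**4. Number of patients.** The documents give no distribution of early-termination days. Assumption: the planning rates of Section 2.3 (20% placebo, 15% active), spread evenly over 700 days, with 267 patients per arm.
- Early terminations: 267 × 0.20 + 534 × 0.15 = 133.5.
- On an off-calendar day, to Day 671: 133.5 × 336/700 ≈ 64.
- On Days 420-447 or 504-531: 133.5 × 56/700 ≈ 10.7, and 10.7/801 = 1.3%. With a common rate of 15% this is 801 × 0.15 × 56/700 = 9.6; with 20% it is 12.8.

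**5. Effect on the model.** Suppose visits up to Week 69 are modelled. Parameters of an unstructured covariance: k(k + 1)/2.
- Weeks 5, 21, 37, 53, 69: k = 5 gives 15.
- Adding Weeks 13, 29, 45, 61: k = 9 gives 45.

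Each early terminator contributes at most one record to the four added levels. The 4 × 3/2 = 6 covariances among those levels therefore have no patient behind them.

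**6. After the change.** With CGI-S in the 16-week column, 0 of the 658 days from 14 to 671 map to a visit off the UHDRS calendar, against 336 now.

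**The case against.** **The schedule of the analysed cohort is not shown.** This stands as a condition. The Protocol Version 3 table belongs to another cohort, is broken in extraction, and has three CGI-S marks between Week 5 and end of treatment where Appendix 1 implies five UHDRS visits. If Protocol Version 6 collects CGI-S 8-weekly, the present column is right and the point falls away.

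**A reader might infer that half of all CGI-S values are affected.** They are not. Scheduled visits keep their labels, and the 49% is a share of possible early-termination days.

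**The Day 430 patient may still have a Week 69 value.** Under the follow-up rule in the Protocol Version 3 synopsis, patients who stop treatment but stay in the study return at Week 69 unless the early-termination visit lies within ±30 days of it. Day 430 is 476 − 430 = 46 days away, so that patient would return. Where the early-termination visit does replace Week 69 (Days 446-506, 61 days), only Days 446, 447, 504, 505 and 506 fall outside 448-503: 5 of 61. This reduces the loss at Week 69 itself; it does not settle how the off-calendar value is treated.

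**A reader might infer that the CGI-S model must fail.** Section 4.4.2 has fallbacks. The realistic result is a move off the unstructured covariance caused by labelling alone, and only if off-calendar levels are modelled.

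**A reader might extend the point to MRI.** SAP Version 1, Appendix 2 says "At Weeks 13, 37, and 69 and at the EoT visit, the MRI should be scheduled to occur before the lumbar puncture", which is not an 8-weekly calendar. But nothing shown establishes that MRI is done at the early-termination visit, so there may be nothing to remap, and BSI is annualized for elapsed time (Section 4.7).

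**A reader might infer that the halt spreads the problem to nearly everyone through Section 5.1.** That section models cUHDRS and its components, which already have the 16-week windows, and "MRI (BSI data, annualized percentage change from baseline"). CGI-S is not in it. Early-termination visits after 22 March 2021 are also outside the main efficacy analysis (Section 4.4).

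**Conclusion.** The point holds for CGI-S, and likewise for PGI-S, on one assumption: that Protocol Version 4 onwards collects them at the UHDRS visits. The column assignment is a stated rule, not a detail left to another document. Under it about half of early-termination CGI-S values (49% of Days 14-643, with termination days taken as uniform) would carry a label at which no CGI-S is scheduled, and the plan has no rule for them.

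The effect on the Week 69 contrast is small: about 11 of 801 patients (1.3%) at planning rates, fewer with return visits or the 22 March 2021 cut-off. The more practical consequences are inconsistent handling of same-day ratings, an open choice between dropping values and adding visit levels, and a possible change of covariance structure. The documents do not support an effect on MRI, on Section 5.1, or on CGI-S values from scheduled visits.

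**What to change.** In Appendix 1, Table 1, after checking the Protocol Version 6 schedule:

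1. Move CGI-S, and any other scale collected on the UHDRS calendar (for example PGI-S), to the UHDRS/CGI-C window column.
2. State that no value is mapped to a visit at which that endpoint is not scheduled.
3. Only if MRI is collected at the early-termination visit, give it its own windows, meeting midway between its scheduled visits.

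The cost is a short edit and a change to the visit-mapping program. There are two small downsides. The wider windows place some values up to 8 weeks from the nominal day. An early-termination value may also be averaged with a labelled visit in the same window; on Day 430, for example, it would be averaged with a later Week 69 rating. The plan already accepts both for UHDRS.
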